### 8.1.3 Supplementary Analyses

A mixed-effects model for repeated measures (MMRM) analysis will be used to estimate the mean change from baseline in the monthly number of headache days of at least moderate severity for the overall 3-month treatment period and by each month to support the primary analysis.

The MMRM will include treatment, sex, country, baseline preventive migraine medication use, month and treatment-by-month interaction as fixed effects and baseline value and years since onset of migraines as covariates. The unstructured covariance structure will be used for repeated observations within a subject. Kenward-Roger approximation will be used to estimate denominator degrees of freedom. The LS means for the treatment groups, LS means for the treatment differences (each TEV-48125 group – placebo group), and corresponding 95% confidence intervals and associated p-values will be calculated by month and for the overall treatment period.

The following SAS code pertains to the MMRM analysis.

```
proc mixed method = reml;
  class USUBJID MONTH TREATMENT SEX PRVMBASE CONTRY;
  model CHG = BASE TTMIG PRVMBASE SEX TREATMENT MONTH
    TREATMENT * MONTH CONTRY /s ddfm = kr;
  repeated MONTH /subject = USUBJID type = un r;
  lsmeans TREATMENT TREATMENT * MONTH / pdiff cl alpha = 0.05;
  ods output diffs = DIFFS lsmeans = LSMEANS;
run;
*PRVMBASE: Baseline preventive medication use
*TTMIG      : Years since onset of migraines
```

If any problems in convergence status arise in the estimation of variance components, heterogeneous Toeplitz, heterogeneous autoregressive of order 1, and heterogeneous compound symmetry, which are error variance-covariance structures, will be applied in that order, and the first structure that achieves convergence will be used. If anything other than an unstructured variance-covariance structure is selected, a sandwich estimator for standard errors will be used.

The LS means  $\pm$  SE of monthly change from baseline values estimated by MMRM will be plotted by month for each treatment group.

Mean change from baseline in the monthly number of headache days of at least moderate severity during the 4-week period after each dose (ie, for Month 1, Month 2, and Month 3) will also be estimated and compared by the same ANCOVA model as described in [Section 8.1.1](#) and by Wilcoxon rank-sum test as described in [Section 8.1.2](#).

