- CT-6.7.3.1.1 Change from Baseline in Monthly Number of Headache Days of at Least Moderate Severity, ANCOVA and Wilcoxon Rank Sum Test, in Male (FAS)
- CT-6.7.3.1.2 Change from Baseline in Monthly Number of Headache Days of at Least Moderate Severity, ANCOVA and Wilcoxon Rank Sum Test, in Female (FAS)
- CT-6.7.3.2.1 Change from Baseline in Monthly Number of Headache Days of at Least Moderate Severity, MMRM, in Male (FAS)
- CT-6.7.3.2.2 Change from Baseline in Monthly Number of Headache Days of at Least Moderate Severity, MMRM, in Female (FAS)
- CT-7.1 Duration of Treatment (Days) and Extent of Exposure to Trial Medication by Country (SS)
- CT-7.2 Number of Doses of Trial Medication by Country (SS)
- CT-7.3 Duration of treatment, n (%) by Country (SS)
- CT-8.1 Summary of AEs by Country (SS)
- CT-8.2.1.1 TEAEs by MedDRA SOC and PT, All Countries (SS)
- CT-8.2.1.2 TEAEs by MedDRA SOC and PT in Japan (SS)
- CT-8.2.1.3 TEAEs by MedDRA SOC and PT in Korea (SS)
- CT-8.2.2.1 Potentially Drug-related TEAEs by MedDRA SOC and PT, All Countries (SS)
- CT-8.2.2.2 Potentially Drug-related TEAEs by MedDRA SOC and PT in Japan (SS)
- CT-8.2.2.3 Potentially Drug-related TEAEs by MedDRA SOC and PT in Korea (SS)

- CT-8.3.1.1 TEAEs by Severity by MedDRA SOC and PT, All Countries (SS)
- CT-8.3.1.2 TEAEs by Severity by MedDRA SOC and PT in Japan (SS)
- CT-8.3.1.3 TEAEs by Severity by MedDRA SOC and PT in Korea (SS)
- CT-8.3.2.1 Potentially Drug-related TEAEs by Severity by MedDRA SOC and PT, All Countries (SS)
- CT-8.3.2.2 Potentially Drug-related TEAEs by Severity by MedDRA SOC and PT in Japan (SS)
- CT-8.3.2.3 Potentially Drug-related TEAEs by Severity by MedDRA SOC and PT in Korea (SS)
- CT-8.4.1.1 TEAEs with an outcome of death by MedDRA SOC and PT, All Countries (SS)
- CT-8.4.1.2 TEAEs with an outcome of death by MedDRA SOC and PT in Japan (SS)
- CT-8.4.1.3 TEAEs with an outcome of death by MedDRA SOC and PT in Korea (SS)
- CT-8.4.2.1 Potentially Drug-related TEAEs with an outcome of death by MedDRA SOC and PT, All Countries (SS)
- CT-8.4.2.2 Potentially Drug-related TEAEs with an outcome of death by MedDRA SOC and PT in Japan (SS)
- CT-8.4.2.3 Potentially Drug-related TEAEs with an outcome of death by MedDRA SOC and PT in Korea (SS)
- CT-8.5.1.1 Serious TEAEs by MedDRA SOC and PT, All Countries (SS)
- CT-8.5.1.2 Serious TEAEs by MedDRA SOC and PT in Japan (SS)
- CT-8.5.1.3 Serious TEAEs by MedDRA SOC and PT in Korea (SS)

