CT-13.5.1	Electronic Columbia-Suicide Severity Rating Scale (eC-SSRS) Assessment Outcome Responses (SS)
CT-13.5.2	Subjects with Positive Responses for Electronic Columbia-Suicide Severity Rating Scale (eC-SSRS) Assessment (SS)
CF-1	LS Mean Change from Baseline in Monthly Number of Headache Days of at Least Moderate Severity Using MMRM (FAS)
CF-2	LS Mean Change from Baseline in Monthly Number of Migraine Days Using MMRM (FAS)
CF-3	LS Mean Change from Baseline in Monthly Number of Days with Use of Any Acute Headache Medication Using MMRM (FAS)
CF-4	LS Mean Change from Baseline in Monthly Number of Headache Days of at Least Moderate Severity in Subjects Not Receiving Concomitant Preventive Migraine Medication Using MMRM (FAS)
PKT-X.1.4.1	Individual and Summary of Plasma Trough Concentration

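### The supplementary MMRM in SAP 8.1.3 fits one baseline slope for all months; a baseline-by-month term would remove a possible, modest distortion of the by-month estimates at almost no cost

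*SAP*

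**What the plan says.** SAP 8.1.3 gives the MMRM, beyond treatment, sex and country, "baseline preventive migraine medication use, month and treatment-by-month interaction as fixed effects and baseline value and years since onset of migraines as covariates". The sample code agrees: "model CHG = BASE TTMIG PRVMBASE SEX TREATMENT MONTH", continued on the next line only by treatment-by-month and country. Baseline enters once, with no BASE*MONTH, so this is the intended model and not a slip in the code. The rest of the model is left free over time: "The unstructured covariance structure will be used for repeated observations within a subject".

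The stated purpose is to estimate change "for the overall 3-month treatment period and by each month to support the primary analysis". The same section adds a second by-month analysis: each month's change "will also be estimated and compared by the same ANCOVA model as described in" Section 8.1.1. Fitted month by month, that ANCOVA has its own baseline slope at each month.

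The MMRM reaches many outputs by cross-reference:
- CT-5.3 and CF-1, "LS Mean Change from Baseline in Monthly Number of Headache Days of at Least Moderate Severity Using MMRM (FAS" (8.1.3)
- CF-2 to CF-4 (8.2.1)
- the exploratory MMRMs, including weekly ones over the first four weeks (8.3)
- the subgroup tables (8.4), for example CT-6.7.3.2.1, "Change from Baseline in Monthly Number of Headache Days of at Least Moderate Severity, MMRM, in Male (FAS"

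Appendix 5 lists titles only. The model is fixed in 8.1.3.

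**The concern.** The model imposes no pattern over time on the covariance, yet it holds the relation between baseline and change constant over time. A screening count may well predict the first month better than the third. If so, one slope is too shallow for some months and too steep for others.

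Two things could follow. Unexplained baseline variation would be left in the Month 3 residual and widen its standard error. And where subjects who leave differ in baseline from those who stay, the model would fill in their Month 3 through the wrong slope and so move the plotted LS means. The MMRM and the monthly ANCOVAs could then disagree because of this constraint, which makes the MMRM harder to read as support for the primary result.

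**Working it through.** **The plan's own figure.** SAP Section 4: difference 1.7 days, SD 4.9, 176 per group, two-sided 0.05. Standard error = 4.9 × √(2/176) = 0.522; 1.7/0.522 = 3.25; 3.25 − 1.96 = 1.29, giving 90.2% power (90.1% with the noncentral t). The stated figure of more than 90% reproduces. It does not involve the MMRM.

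**The constraint.** As specified, the mean of CHG for subject i in month j is μ(treatment, j) + β·BASE + other covariates. The alternative replaces β by β_j. If the true slopes differ, the Month 3 residual under the common slope carries an extra (β_3 − β)·BASE, which adds (β_3 − β)²·Var(BASE) to its variance.

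**Simulation 1.** Assumptions not in the SAP: slopes of change on baseline at Months 1/2/3 either equal (−0.35 each), moderately diverging (−0.25/−0.35/−0.45) or strongly diverging (−0.15/−0.35/−0.55); baseline SD 5.5; between-month residual correlation 0.75; log-odds of dropout 0.7 per baseline SD where dropout depends on baseline. From the SAP: 180 per arm, three arms, and the SD of the average change scaled to 4.9. There were 300 trials per scenario, fitted with and without BASE*MONTH, with the other covariates omitted.

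Check by hand with no dropout, taking the common slope as the mean, −0.35:
- Strong: extra variance 0.20² × 5.5² = 1.21. On the difference, 2 × 1.21/180 = 0.0134. With BASE*MONTH the standard error was 0.521, so √(0.521² + 0.0134) = 0.534, ratio 1.02. Simulated: 1.025.
- Moderate: 0.10² × 5.5² = 0.30; 2 × 0.30/180 = 0.0034; √(0.518² + 0.0034) = 0.521, ratio 1.006. Simulated: 1.006.

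Common-slope model minus (or divided by) the BASE*MONTH model:

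| Slopes | Missing at Month 3 | Dropout depends on baseline | Shift, placebo LS mean (days) | Shift, treatment difference (days) | SE ratio, Month 3 difference |
|---|---|---|---|---|---|
| Moderate | 0% | – | −0.001 | 0.002 | 1.006 |
| Moderate | 11.7% | all arms alike | 0.069 | 0.002 | 1.009 |
| Moderate | 11.0% | active arms only | 0.003 | 0.063 | 1.008 |
| Moderate | 21.6% | all arms alike | 0.131 | 0.005 | 1.011 |
| Moderate | 20.7% | active arms only | 0.001 | 0.133 | 1.010 |
| Strong | 0% | – | −0.009 | 0.013 | 1.025 |
| Strong | 11.7% | all arms alike | 0.135 | −0.003 | 1.036 |
| Strong | 10.8% | active arms only | −0.001 | 0.131 | 1.035 |
| Strong | 21.6% | all arms alike | 0.260 | −0.005 | 1.046 |
| Strong | 20.8% | active arms only | −0.002 | 0.270 | 1.043 |

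With equal slopes the shifts were 0 and the SE ratio 1.00. With dropout running in opposite directions by arm (about 22%), an extreme case, the difference moved by 0.264 (moderate) or 0.525 day (strong). The SE ratio for the overall three-month contrast never exceeded 1.006.

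**Simulation 2.** Assumptions: two arms of 180, baseline SD 6, monthly SD 6.5, true difference −1.70. With complete data, the variance ratios at Month 3 convert to SE ratios by square root:
- correlations of baseline with Months 1/2/3 of 0.70/0.65/0.60: √1.005 = 1.002
- 0.75/0.65/0.55: √1.039 = 1.019
- 0.80/0.65/0.50: √1.119 = 1.058
- 0.80/0.60/0.40: √1.243 = 1.115

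With 12% dropout on placebo (more in severe subjects) and 7% on active (unrelated to baseline), the Month 3 difference averaged −1.789 and −1.826 for the two middle patterns under the common slope, against −1.692 in both with BASE*MONTH. The three-month averages were −1.742 and −1.757, against −1.701 and −1.700.

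**The case against.** The strongest reply is that this is a clearly stated choice in a supplementary model, and that the primary conclusion does not depend on it. That stands. The primary test is the ANCOVA of the 12-week average (8.1.1). Section 14 gives the task of exploring missing data to multiple imputation, and lists the MMRM only as added to estimate overall and by-month change.

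The second reply is that the monthly ANCOVAs already allow a slope per month, and in Simulation 1 the Month 3 ANCOVA showed essentially no bias. This stands in part. Dropout in that simulation depended only on baseline. The monthly ANCOVA uses only subjects observed in that month and cannot draw on their earlier months, and none of the planned figures comes from it.

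Third, BASE*MONTH would not make the two by-month analyses identical: separate ANCOVAs also let the effects of sex, country, preventive use and years since onset vary by month. That is correct, so the term removes one source of disagreement and not all of them.

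A reader might infer that precision is certainly lost, or that the figures are tilted towards the drug. The documents support neither. The SAP gives no slopes, correlations or dropout rate. The direction depends on the arm in which dropout tracks baseline: in the simulations the difference moved in the drug's favour when this was placebo, and against it when it was the active arms.

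**Conclusion.** The point holds as a near-free improvement to a supplementary analysis. The MMRM in 8.1.3 assumes one baseline slope for all months, and every output that refers to it inherits the assumption.

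The size is conditional, in steps:
- Slopes equal over time: no effect.
- Slopes diverging: Month 3 standard error up by about 0–5% in Simulation 1, and by about 11% in the most extreme pattern of Simulation 2, where the baseline correlation halves from 0.80 to 0.40.
- Dropout also dependent on baseline: Month 3 LS means off by about 0.07–0.26 day.
- That dependence also different by arm: Month 3 difference off by about 0.06–0.27 day. Against the standard errors in those scenarios this is 0.063/0.538 = 12% to 0.270/0.572 = 47% of one standard error; against the planning effect it is 0.063/1.7 = 4% to 0.270/1.7 = 16%.

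All of these figures rest on assumed slopes, correlations and dropout. It would go too far to read the point as a threat to the primary result, the stated power or the multiple-imputation analysis, since none of them uses this model. The Month 3 figures also do not describe the weekly models, which cover only the first four weeks. There the same constraint applies across weeks, and its size was not examined.

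**What to change.** In SAP 8.1.3, add the baseline-by-month interaction to the list of MMRM terms and BASE*MONTH to the MODEL statement. State that the weekly MMRMs in 8.3.1 and 8.3.2 use BASE*WEEK. Appendix 5 needs no edit: CF-1 to CF-4, the MMRM tables and the subgroup tables follow by cross-reference. The LSMEANS statement is unchanged, and no new data are needed.

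The cost is two degrees of freedom in the three-month models and three in the four-week models. That is negligible with 540 subjects, and for CF-4 too: with concomitant preventive use capped at 30% (3.3.1), at least 0.70 × 540 = 378 planned subjects remain. It will be slightly more noticeable in small subgroups such as males, whose number the SAP does not give. The change should be made before unblinding.

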## **Appendix 6 List of Subject Data Listings**

PDATA-1	Subject Disposition (RS)
PDATA-2	Analysis Population Flag (RS)
PDEV-1	Major Protocol Deviations (RS)
DEMOG-1	Demographics (RS)
DEMOG-2	Initial Migraine Diagnosis Date (RS)
DEMOG-3	Childbearing Potential (Females Only) (RS)
PDATA-3	Medical History (RS)
PDATA-4	Complications (RS)
PDATA-5.1	Prior and Concomitant Medications and Therapy (RS)
PDATA-5.2	Past Preventive Migraine Medications (RS)
SMED-1	Study Drug Administration (RS)
SMED-2	Extent of Exposure (RS)
PDATA-6	Vital Signs Values (RS)
PDATA-7.1	Electrocardiogram Measurement (RS)
PDATA-7.2	Electrocardiogram Interpretation (RS)
PDATA-7.3	Electrocardiogram Findings (RS)
PDATA-7.4	Electrocardiogram Technical (RS)

PDATA-8	Physical Examination Findings (RS)
PDATA-9	Electronic Columbia-Suicide Severity Rating Scale (eC-SSRS) Assessment (RS)
PDATA-10	Injection Site Assessment (RS)
PDATA-11	Screen Failures (Screen Failure)
PDATA-12	Subjects Who Did Not Meet Inclusion Criteria or Meet Exclusion Criteria (Screen Failure)
PDATA-13	Pharmacokinetic Blood Draw Date and Times (RS)
PDATA-14	Anti-drug Antibodies Blood Draw Date and Times (RS)
PDATA-15	Biomarker Sampling Date and Times (RS)
PDATA-16	Subjects Who Did Not Meet Inclusion Criteria or Meet Exclusion Criteria (RS)
PDATA-17	Information on Subjects Lost to Follow-up (RS)
EFF-1.1	Electronic Headache Diary Questionnaire - Questions List
EFF-1.2	Electronic Headache Diary Questionnaire - Results (RS)
EFF-1.3	Electronic Headache Diary Questionnaire - Derived (RS)
EFF-2.1	6-Item Headache Impact Test (HIT-6) - Questions List
EFF-2.2	6-Item Headache Impact Test (HIT-6) - Results (RS)
EFF-3.1	Migraine-Specific Quality of Life (MSQOL) Questionnaire - Questions List
EFF-3.2	Migraine-Specific Quality of Life (MSQOL) Questionnaire - Results (RS)
EFF-4.1	EuroQoL-5 Dimension (EQ-5D-5L) Questionnaire - Questions List
EFF-4.2	EuroQoL-5 Dimension (EQ-5D-5L) Questionnaire - Results (RS)
EFF-5.1	Patient Health Questionnaire-9 (PHQ-9) - Questions List
EFF-5.2	Patient Health Questionnaire-9 (PHQ-9) - Results (RS)
EFF-6.1	Work Productivity and Activity Impairment (WPAI) Questionnaire - Questions List
EFF-6.2	Work Productivity and Activity Impairment (WPAI) Questionnaire - Results (RS)
EFF-7	Patients Global Impression of Change (PGIC) Scale (RS)
AE-1	Treatment-Emergent Adverse Events (RS)
AE-2	Prior to Treatment Adverse Events (RS)
LAB-1	Serum Chemistry Laboratory Tests Results (RS)
LAB-2	Hematology Laboratory Tests Results (RS)
LAB-3	Coagulation Laboratory Tests Results (RS)
LAB-4	Urinalysis Laboratory Tests Results (RS)

Protocol 406-102-00001

LAB-5                      Pregnancy Test Results (Females Only) (RS)
